6.4.2 Permitted concomitant therapy requiring caution

Not Applicable

6.4.3 Prohibited concomitant therapy

Ibrutinib is primarily metabolized by CYP3A. The concomitant use of CYP3A inhibitors or inducers is likely to alter the exposure of ibrutinib, therefore moderate to strong CYP3A inhibitors and strong CYP3A inducers should not be used during this study. Please refer to the ibrutinib package insert for additional information.

6.4.4 Use of Bisphosphonates (or other concomitant agents)

Not applicable.

6.5 Patient numbering, treatment assignment or randomization

6.5.1 Patient numbering

Each patient is identified in the study by a Subject Number (Subject No.), that is assigned when the patient is first enrolled for screening and is retained as the primary identifier for the patient throughout his/her entire participation in the trial. The Subject No. consists of the Center Number (Center No.) (as assigned by Novartis to the investigative site) with a sequential patient number suffixed to it, so that each subject is numbered uniquely across the entire database. Upon signing the informed consent form, the patient is assigned to the next sequential Subject No. available to the investigator through the clinical database.

6.5.2 Treatment assignment or randomization

The assignment of a patient to a particular cohort will be coordinated by Novartis or designee.

6.5.3 Treatment blinding

Not applicable

6.6 Study drug preparation and dispensation

The investigator or responsible site personnel must instruct the patient or caregiver to take ibrutinib as per protocol. Ibrutinib will be dispensed to the patient by authorized site personnel only. VAY736 will be given as an IV infusion at the study center. For specifics on the administration of VAY736, see the Pharmacy Manual. All dosages prescribed to the patient and all dose changes during the study must be recorded on the Dosage Administration Record CRF.

Instructions for the preparation and storage conditions are described in the pharmacy manual.

6.6.1 Study treatment packaging and labeling

VAY736, will be provided as open label bulk medication and will be packed and labeled under the responsibility of Novartis, Drug Supply Management.

Ibrutinib, will be sourced as local commercial supply (in the locally approved formulation and packaging configuration) and labeled in the country when possible.

Study treatment labels will comply with the legal requirements of each country and will include storage conditions, a unique medication number (corresponding to study treatment and strength) or randomization number if appropriate.

The storage conditions for study drug will be provided on the label.

6.6.2 Drug supply and storage

Study treatments must be received by designated personnel at the study site, handled and stored safely and properly, and kept in a secured location to which only the investigator and designated site personnel have access. Upon receipt, the study treatment should be stored according to the instructions specified on the drug labels and in the [Investigator's Brochure].

6.6.3 Study drug compliance and accountability

6.6.3.1 Study drug compliance

Compliance will be assessed by the investigator and/or study personnel at each patient visit and information provided by the patient and/or caregiver will be captured in the Drug Accountability Form. This information must be captured in the source document at each patient visit.

6.6.3.2 Study drug accountability

The investigator or designee must maintain an accurate record of the shipment and dispensing of study treatment (VAY736 and ibrutinib) in a drug accountability log. Drug accountability will be noted by the field monitor during site visits and at the completion of the study. Patients will be asked to return all unused study treatment and packaging on a regular basis, at the end of the study or at the time of study treatment discontinuation.

At study close-out, and, as appropriate during the course of the study, the investigator will return all used and unused study treatment, packaging, drug labels, and a copy of the completed drug accountability log to the Novartis monitor or to the Novartis address provided in the investigator folder at each site.

6.6.3.3 Handling of other study treatment

Not applicable.

6.6.4 Disposal and destruction

The site may destroy and document destruction of unused study treatment, drug labels and packaging as appropriate in compliance with site processes, monitoring processes, and per local regulation/guidelines. Otherwise, the investigator will return all unused study treatment, packaging, drug labels, and a copy of the completed drug accountability log to the Novartis monitor or to the Novartis address provided in the investigator folder at each site.

7 Visit schedule and assessments

7.1 Study flow and visit schedule

Table 7-1 and Table 7-2 list all of the assessments and indicate with an “X”, the visits when they are performed. Unscheduled testing may be conducted as necessary to address safety concerns. All data obtained from these assessments must be supported in the patient’s source documentation. The table indicates which assessment produce data to be entered into the database (D) or remain in source documentation only (S) (Category column). No CRF will be used as a source document.

C1D1 assessments can be conducted within 3 days prior to C1D1. On treatment assessments can be conducted within 3 days prior to the planned assessment. If screening assessments are conducted within 3 days of C1D1, they do not need to be repeated for C1D1.

After C1D1, tests and/or procedures should occur on schedule whenever possible. A visit window of +/- 3 days is allowed for assessments except imaging and PK. For PK samples, with the exception of collection(s) made on Day 1 (corresponding with dosing), if PK assessment must be delayed for scheduling purposes, it is mandatory that the correct date and time of the collection are captured in the eCRF. On PK collection days, the time windows are provided in [Table 7-6](#), [Table 7-7](#), and [Table 7-8](#). In situations when dosing is delayed, PK collections should also be delayed until the subsequent dose is given. See [Section 7.2.1](#) for windows on imaging.

Table 7-1 Visit evaluation schedule for Q2W VAY736 dosing regimen

	Category	Protocol Section	Screening	Cycle 1		Cycle 2		Cycle 3		Cycle 4		Subsequent cycles		End of study treatment (EoT)	30-day Follow up	TTP	
				1	2	4	8	15	1	15	1	2	4	8	15	1	15
Day of cycle																	
Obtain Informed Consent	D	7.1.1.1	X														
Demography	D	7.1.1.2	X														
Inclusion/exclusion criteria	D	5	X														
Relevant medical history/current medical conditions	D	7.1.1.2	X														
Diagnosis and extent of cancer	D	7.1.1.2	X														
Prior antineoplastic therapy	D	7.1.1.2	X														
Antineoplastic therapies since discontinuation of study treatment	D	7.1.2														X	X
Prior/concomitant medications	D	7.1.1.2	X													Continuous	

Physical examination	S	7.2.2.1	X	X			X	X		X			X		X (Q3M after C9)			
Performance status	D	7.2.2.4	X	X				X		X			X		X (Q3M after C9)		X	
Height	D	7.2.2.3	X															
Weight	D	7.2.2.3	X	X			X	X		X			X		X (through C6 or through C8 if continuing VAY736 treatment)			
Vital signs	D	7.2.2.2	X	X				X	X				X		X			
Laboratory assessments		7.2.2.5																
Hematology	D	7.2.2.5.1	X	X	X	X	X	X	X	X			X	X	X (Q3M after C9)	X (C5&C6) (Additionally C7&C8 if continuing VAY736 treatment)	X	
Chemistry	D	7.2.2.5.2	X	X	X	X	X	X	X	X			X	X	X (Q3M after C9)	X (C5&C6) (Additionally C7&C8 if continuing VAY736 treatment)	X	
Direct and indirect Coomb's test	D	7.2.2.5	X															
B2-microglobulin	D	7.2.2.5	X															
Quantitative immunoglobulins	D	7.2.2.5	X							X					X (C6& C9)			

Thyroid Panel	D	7.2.2.5	X																
Coagulation	D	7.2.2.5	X	X															X
Urinalysis	D	7.2.2.5.3	X																
Efficacy assessment																			
Radiologic ¹ evaluation	D	7.2.1	X											X		X (C9)	X(C6)		X
Safety	D																		
Adverse events	D	8	X													Continuous			

VAY736 administration	D	6.1.1		X		X	X	X	X		X	X	X	X (through C6 if the patient has no evidence of disease at the radiological assessment and normal blood counts at C6D15 or through C8 if there is evidence of disease at the radiological assessment or abnormal blood counts at C6D15)	X (through C6 if the patient has no evidence of disease at the radiological assessment and normal blood counts at C6D15 or through C8 if there is evidence of disease at the radiological assessment or abnormal blood counts at C6D15)					
Ibrutinib administration	D	6.1.1 & 7.1.2																		
PK sampling (VAY736)	D	7.2.3.1		X	X	X	X	X	X	X	X	X	X	X (C5, C6 only) (Additionally C7, C8 if continuing VAY736 treatment)	X (C5 & C6 only) (Additionally C7, C8 if continuing VAY736 treatment)	X				

Table 7-2 Visit evaluation schedule for Q4W VAY736 dosing regimen

	Category	Protocol Section	Screening	Cycle 1					Cycle 2		Cycle 3					Cycle 4		Subsequent cycles		End of study treatment (EoT)	30-day Follow up	TTP
				1	2	4	8	15	1	15	1	2	4	8	15	1	1	15				
Day of cycle																						
Physical examination	S	7.2.2.1	X	X					X	X		X				X	X (Q3M after C9)					
Performance status	D	7.2.2.4	X	X					X		X					X	X (Q3M after C9)		X			
Height	D	7.2.2.3	X	X																		
Weight	D	7.2.2.3	X	X					X		X					X	X (through C6 or through C8 if continuing VAY736 therapy)					
Vital signs	D	7.2.2.2	X	X					X	X						X	X					
Laboratory assessments																						
Hematology	D	7.2.2.5.1	X	X	X	X			X	X						X	X (Q3M after C9)	X (C6)	X			
Chemistry	D	7.2.2.5.2	X	X	X	X			X	X						X	X (Q3M after C9)	X (C6)	X			
Direct and Indirect Coomb's test	D	7.2.2.5	X																			
B2-microglobulin	D	7.2.2.5	X																			
Quantitative immunoglobulins	D	7.2.2.5	X								X						X (C6& C9)					
Thyroid Panel	D	7.2.2.5	X																			
Coagulation	D	7.2.2.5	X	X														X				

	Category	Protocol Section	Screening	Cycle 1					Cycle 2		Cycle 3					Cycle 4		Subsequent cycles			End of study treatment (EoT)	30-day Follow up	TTP
Day of cycle				1	2	4	8	15	1	15	1	2	4	8	15	1		1	15				
Urinalysis	D	7.2.2.5.3	X																				
Efficacy assessment																							
	D	7.2.1	X													X		X (C9)	X(C6)			X	
Ibrutinib resistance mutation	D	7.2.2.7	X													X		X (C7 & C9)				X	
ECG	D	7.2.2.6.1	X																X				
Safety																							
Adverse events	D	8	X													Continuous							

	Category	Protocol Section	Screening	Cycle 1					Cycle 2		Cycle 3					Cycle 4		Subsequent cycles		End of study treatment (EoT)	30-day Follow up	TTP
Day of cycle				1	2	4	8	15	1	15	1	2	4	8	15	1	1	15				
VAY736 administration	D	6.1.1		X					X		X					X		X (through C6 if the patient has no evidence of disease at the radiological assessment and normal blood counts at C6D15 or through C8 if there is evidence of disease at the radiological assessment or abnormal blood counts at C6D15)				
Ibrutinib administration	D	6.1.1 & 7.1.2		Continuous daily dosing through C9D1																		
PK sampling (VAY736)	D	7.2.3.1		X	X	X	X	X	X		X	X	X	X	X	X	X	X (C5, C6)		X		

	Category	Protocol Section	Screening	Cycle 1					Cycle 2		Cycle 3					Cycle 4		Subsequent cycles		End of study treatment (EoT)	30-day Follow up	TTP
Day of cycle				1	2	4	8	15	1	15	1	2	4	8	15	1	1	15				
																			(Additionally C7, C8 if continuing VAY736 treatment)			
PK sampling (ibrutinib)	D	7.2.3.1		X	X		X		X		X					X		X (through C6 or through C8 if continuing VAY736 treatment)		X		
VAY736 Ig	D	7.2.3.1		X			X	X		X						X		X (through C6 or through C8 if continuing VAY736 treatment)		X		
End of study	D	7.1.5																		X	X	

7.1.1 Screening

Screening starts after a patient has provided written informed consent to participate in the study and ends on the day of the first dose of VAY736 and ibrutinib. Screening assessments have to be done within 21 days prior to the first dose with the exception of baseline tumor assessments and informed consent. Screening tumor assessments collection can be conducted within 28 days of first dose and informed consent can be obtained within 3 months of the first dose. Assessments conducted prior to obtaining informed consent as a part of routine disease care can be used to satisfy eligible criteria as long as the procedures were performed within the allowed windows.

7.1.1.1 Information to be collected on screening failures

Patients who sign an informed consent but fail to be started on VAY736 for any reason will be considered a screen failure. The reason for not being started on treatment will be entered on the Screening Phase Disposition Page. The demographic information, informed consent, and Inclusion/Exclusion pages must also be completed for Screen Failure patients. No other data will be entered into the clinical database for patients who are screen failures, unless the patient experienced a Serious Adverse Event during the Screening Phase (see [Section 8](#) for SAE reporting details).

7.1.1.2 Patient demographics and other baseline characteristics

Participant demographics: full date (only if required and permitted) or year of birth or age, sex, race/predominant ethnicity (if permitted) and relevant medical history/current medical conditions (until date of signature of informed consent) will be recorded in the eCRF. Where possible, the diagnosis and not symptoms should be recorded. Participant race/ethnicity data are collected and analyzed to identify any differences in the safety and/or efficacy profile of the treatment due to these characteristics. In addition, the diversity of the study population needs to be assessed as required by Health Authorities.

7.1.2 Treatment period

The study treatment period for each patient begins when the patient receives the first dose of VAY736 in combination with ibrutinib and ends at C9D1. Patients will receive the combination of VAY736 and ibrutinib for six cycles. Patients will continue VAY736 for 2 additional cycles in combination with ibrutinib if there is evidence of disease at the radiological assessment or abnormal blood counts defined by IWCLL response criteria at C6D15. For the purpose of scheduling and evaluations, a treatment cycle is 28 days. VAY736 will be discontinued at C7D1 if the patient shows a complete radiological response or normal blood counts at C6D15 and ibrutinib will continue for an additional 2 cycles. All patients will have final response assessment [REDACTED]. Further treatment or follow-up will depend on status of response at C9D1. One of the following actions will be taken for patients:

- Patients who experience disease progression at C9D1 (or any time prior to C9D1) will discontinue treatment and will have required end of treatment assessments conducted.
- Patients whose disease is assessed as stable disease, partial response, at C9D1 may continue ibrutinib and will be followed every 3 months for two years for TTP assessments,

with the exception of CT scans which will be performed every 6 months unless the patient experiences disease progression or the administration of a new therapy. If the patient continues to receive ibrutinib past C9D1, the details of administration will be recorded on the Antineoplastic therapies since discontinuation eCRF.

- For patients whose disease is assessed as CR at C9D1, investigators may consider discontinuing ibrutinib, and be followed every 3 months for two years for TTP assessments, with the exception of CT scans which will be performed every 6 months unless the patient experiences disease progression or the administration of a new therapy. Although investigators may consider discontinuing ibrutinib if patients have a CR at C9D1, if the patient continues to receive ibrutinib past C9D1, the details of administration will be recorded on the Antineoplastic therapies since discontinuation eCRF.

Patients who discontinue one of the combination drugs (ibrutinib or VAY736) prior to six cycles of treatment for reasons other than disease progression may continue the other drug until the end of treatment period (VAY736 until C6D28 or ibrutinib until C8D28). All patients regardless of study treatment duration, who have not progressed, will have a final disease assessment at C9D1 (end of treatment period).

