Patients will receive the combination of VAY736 and ibrutinib for 6 cycles. Starting with C7D1, VAY736 will be discontinued if the patient has achieved a CR per IWCLL response criteria with no evidence of disease per radiological assessment and normal blood counts at C6D15. Ibrutinib will be administered per protocol for an additional two cycles (through C8D28). If a patient has not achieved a CR per IWCLL response criteria at C6D15, VAY736 and ibrutinib will be continued for 2 additional cycles (Cycle 7 and Cycle 8). At C9D1 (± 7 days), patients will have their final disease assessment [REDACTED] of the study. All patients who have remained on study, including those who have discontinued treatment due to reasons other than disease progression, will be assessed at this time point. For patients who achieve a complete response at this assessment, investigators may consider discontinuing ibrutinib in order to follow patients for durability of response and minimize intolerance and toxicity associated with continuous ibrutinib therapy while maximizing patient quality of life.

Figure 4-1 Study design

* Combination administered for either 6 cycles or 8 cycles, ibrutinib continued through C8D28. For patients who achieve a CR at the primary endpoint (C9D1), investigators may consider discontinuing ibrutinib.

**Patients will be evaluated for the final disease assessment on C9D1 (\pm 7 days) in accordance with IWCLL guidelines.

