6.1.5 Treatment duration

Patients will receive VAY736 and ibrutinib in combination for up to a total of six cycles. Patients will continue on VAY736 and ibrutinib therapy for Cycle 7 and Cycle 8 if the patient has evidence of disease at the radiological assessment or abnormal blood counts defined by IWCLL response criteria at C6D15. Starting with C7D1, VAY736 will be discontinued if the patient has no evidence of disease in radiological assessment and normal blood at C6D15 and ibrutinib will be administered for the next two cycles. [REDACTED]

[REDACTED] Further treatment with ibrutinib is dependent upon the outcome of the assessment that is conducted at C9D1 (see [Section 7.1.2](#)).

Patients may be discontinued from treatment with the study drug(s) earlier due to unacceptable toxicity, disease progression and/or at the discretion of the investigator or the patient. Patients, who discontinue VAY736 for reasons other than disease progression prior to 6 cycles of treatment, may continue with ibrutinib through the C9D1 assessment. Patients who discontinue ibrutinib for reasons other than disease progression prior to 6 cycles of treatment may continue with VAY736 through cycle 6 and have a disease assessment at C9D1. Patients who have disease progression and who have evidence of clinical benefit, such as disease shrinkage at other sites or symptomatic improvement, may continue treatment with the agent(s) being administered at the time disease progression is recorded. In addition, treatment may be temporarily interrupted to permit local therapy for symptomatic metastases after disease progression has been documented. Patients who continue on treatment after disease progression should discontinue study treatment once they are no longer deriving benefit as assessed by the investigator.

A patient who has experienced an interruption of more than 28 days of either one or both drugs may remain on study if the patient has experienced clinical benefit and the investigator believes it is in the best interest of the patient to remain on study and such action is agreed to by Novartis. Both the decision and documentation of the discussion with Novartis, must be available in the source documentation and described as an investigator comment in the eCRF.

[REDACTED]

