7.1.5 Follow up for safety evaluations

All patients will be followed for a 30 day safety follow-up period subsequent to completion of VAY736 therapy. Patients who continue on ibrutinib after the discontinuation of VAY736 regardless of when this occurred will be followed for safety according to the ibrutinib package insert. No new AEs or SAEs will be collected beyond the 30 day safety follow-up or during the two-year efficacy follow up period. Any data that is collected should be added to the Adverse Events CRF and the Concomitant Medications CRF. The end of study eCRF should be

completed after the patient has discontinued from the study, either after the 30 day safety follow-up period or at progression that occurs during the two-year efficacy follow-up.

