8.2.2 Reporting

For patients who sign the main study ICF, SAE collection starts at the time of main study informed consent, whether the patient is screen failure or not.

To ensure patient safety, every SAE, regardless of suspected causality, occurring after the patient has provided informed consent and as outlined in [Section 7.1.5](#) must be reported to Novartis within 24 hours of learning of its occurrence. If a patient starts a post-treatment antineoplastic therapy, then only SAEs suspected to be related to study treatment will be reported.

Any additional information for the SAE including complications, progression of the initial SAE, and recurrent episodes must be reported as follow-up to the original episode within 24 hours of the investigator receiving the follow-up information. An SAE occurring at a different time interval or otherwise considered completely unrelated to a previously reported one should be reported separately as a new event.

Any SAEs experienced after the 30 day safety evaluation follow-up period should only be reported to Novartis if the investigator suspects a causal relationship to the study treatment.

Information about all SAEs is collected and recorded on the Serious Adverse Event Report Form; all applicable sections of the form must be completed in order to provide a clinically thorough report. The investigator must assess and record the relationship of each SAE to each specific study treatment (if there is more than one study treatment), complete the SAE Report Form in English, and submit the completed form within 24 hours to Novartis. Detailed instructions regarding the SAE submission process and requirements for signatures are to be found in the investigator folder provided to each site.

Follow-up information is submitted in the same way as the original SAE Report. Each re-occurrence, complication, or progression of the original event should be reported as a follow-up to that event regardless of when it occurs. The follow-up information should describe whether the event has resolved or continues, if and how it was treated, whether the blind was broken or not, and whether the patient continued or withdrew from study participation.

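### Protocol Section 7.1.2 tells sites both to stop and to continue VAY736 after Cycle 6 when radiology and blood counts disagree at C6D15

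*Protocol*

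**What the plan says.** Section 7.1.2 of the protocol contains two rules for the C6D15 decision. VAY736 goes on for two more cycles "if there is evidence of disease at the radiological assessment or abnormal blood counts defined by IWCLL response criteria at C6D15". Two sentences later, "VAY736 will be discontinued at C7D1 if the patient shows a complete radiological response or normal blood counts at C6D15".

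Four other places state the stop condition, all with *and*:

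- Section 6.1.5: "VAY736 will be discontinued if the patient has no evidence of disease in radiological assessment and normal blood at C6D15".
- Section 4.1 stops VAY736 for a patient who has reached "a CR per IWCLL response criteria with no evidence of disease per radiological assessment and normal blood counts at C6D15", and continues it for a patient not in CR.
- Tables 7-1 (Q2W) and 7-2 (Q4W) use the same words in the VAY736 administration row: "through C6 if the patient has no evidence of disease at the radiological assessment and normal blood counts at C6D15".

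Three further provisions bear on the consequence. Section 7.1.5 follows patients for 30 days after VAY736 is completed and adds: "No new AEs or SAEs will be collected beyond the 30 day safety follow-up". Section 8.2.2 keeps an exception for later SAEs, which "should only be reported to Novartis if the investigator suspects a causal relationship to the study treatment". On efficacy, Section 7.1.2 states: "All patients regardless of study treatment duration, who have not progressed, will have a final disease assessment at C9D1".

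**The concern.** A stop rule and a continue rule that decide the same question should be complements: every patient meets exactly one. In Section 7.1.2 both are joined by *or*, so they overlap for any patient whose radiology and counts disagree. Either action then breaches one sentence of the section. Section 12 does not let the sponsor authorise deviations, and no text says which section prevails.

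Such patients are foreseeable. Eligibility (Section 5.2) admits platelets from 25 × 10⁹/L and hemoglobin from 8 g/dL, whereas CR in Table 14-1 needs at least 100 × 10⁹/L and 11 g/dL. The SAP's CRi category (Table 5-1) describes patients who meet all other CR criteria but have a persistent cytopenia.

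At stake is the planned amount of VAY736 before the C9D1 response assessment. Under Section 7.1.5, so is the length of adverse event collection. Safety and tolerability are primary objectives, so neither should depend on which sentence a site happened to follow.

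**Working it through.** **Logic of the rule.** Let R mean radiology clear at C6D15 and B mean counts normal at C6D15, treating a complete radiological response as the absence of radiological disease.

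- Continue sentence, Section 7.1.2: (not R) or (not B).
- Stop sentence, Section 7.1.2: R or B.
- Stop wording in Section 6.1.5 and Tables 7-1 and 7-2: R and B.

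| Radiology | Counts | 7.1.2 continue sentence met | 7.1.2 stop sentence met (*or*) | Stop met if joined by *and* |
|---|---|---|---|---|
| clear | normal | no | yes | yes |
| clear | abnormal | yes | yes | no |
| not clear | normal | yes | yes | no |
| not clear | abnormal | yes | no | no |

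As written, two of the four states meet both rules. With *and*, stop and continue are exact complements and no state overlaps. These are logical states, not patient proportions.

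**Section 4.1 is a second, separate mismatch.** CR in Table 14-1 also requires a normal marrow and no constitutional symptoms. A patient with clear radiology and normal counts who is not in CR would continue under Section 4.1 but stop under Section 6.1.5. That patient is not discordant in the sense of the table above, so correcting the conjunction in Section 7.1.2 would not settle the case.

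**Consequence per discordant patient.** Inputs: 28-day cycles, with Q2W infusions on Days 1 and 15 (Section 6.1.1), and 30 days of follow-up after VAY736 (Section 7.1.5). Assumptions: no holds, delays or early stops, and the 30 days run from the last planned infusion.

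- Planned infusions: 6 × 2 = 12, or 8 × 2 = 16.
- Last infusion with 6 cycles: C6D15 = 5 × 28 + 15 = day 155. Collection ends at 155 + 30 = day 185.
- Last infusion with 8 cycles: C8D15 = 7 × 28 + 15 = day 211. Collection ends at 211 + 30 = day 241.
- C9D1 = 8 × 28 + 1 = day 225.
- With 6 cycles, collection ends 225 − 185 = 40 days before C9D1. With 8 cycles, it ends 241 − 225 = 16 days after. The gap is 241 − 185 = 56 days.

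**Sensitivity to the anchor.** Counting from the end of the last VAY736 cycle instead gives 6 × 28 + 30 = day 198 (27 days before C9D1) or 8 × 28 + 30 = day 254 (29 days after). The gap is still 56 days. On Q4W the planned infusions are 6 or 8, and the gap is again two 28-day cycles.

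**The case against.** The strongest reply is that this is one stray conjunction. The continue sentence of Section 7.1.2, Section 6.1.5, both visit schedules and Section 4.1 all give the same answer for a discordant patient, so a site reading the whole protocol would probably see a drafting slip. That limits how often the conflict would change practice. It does not remove it, because this sentence is an operative treatment-duration rule, and weighing it against the other places is inference rather than an instruction.

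A second reply concerns adverse events. The 56-day difference comes from 6 versus 8 cycles, which the protocol plans anyway; the ambiguity only affects which duration applies. This is correct. It is also argued that Section 10.5.3.1 runs the on-treatment period to 30 days after the last study medication. With ibrutinib planned through C8D28, that would give the same end date either way. But Section 10.5.3.1 defines an analysis period. For monitoring, Section 8.1.1 refers to Section 7.1.5, which counts from completion of VAY736. The day counts therefore stand, conditional on that reading and the stated anchor.

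A third reply is that early termination, recorded in SAP Section 1, may leave the amendment with no remaining use. The documents do not say whether any patient has yet to reach C6D15, so this stays open.

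**Conclusion.** The contradiction is real and lies in the current text. Under Section 7.1.2, every patient with exactly one of radiology and counts clear at C6D15 meets both the stop and the continue rule. For such a patient on Q2W, 12 or 16 infusions are planned and the end of adverse event collection moves by 56 days. The calendar dates (day 185 or 241) assume uninterrupted dosing and 30 days counted from the last planned infusion. How many patients are affected cannot be derived from the documents.

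The reach is limited. Suspected-related SAEs are still reported after the 30 days. The SAP on-treatment window (Section 2.1.1.5) is always determined, because it uses the last actual VAY736 administration. C9D1 is assessed whatever the treatment duration. Neither Cycle 1 DLT/MTD estimation nor the C9 CR/CRi analysis method changes. It should be corrected, but it does not undermine the primary dose-finding analysis.

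**What to change.** Reconcile Section 7.1.2 (both sentences), Section 4.1, Section 6.1.5 and Tables 7-1 and 7-2 so that one criterion, worded identically, governs stopping and its exact complement governs continuing. The wording should say whether the decision rests on radiology plus counts or on full IWCLL CR. The clinical choice belongs to the sponsor's clinical team.

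The cost is a written amendment with the approvals in Section 12.1. The number of sentences to change depends on the criterion chosen. Section 6.1.5 and the two tables already agree in substance, but differ slightly in wording.

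Optionally, add C6D15 radiology and count status, as description only, to the VAY736 C7–C9 disposition output (SAP Section 2.3.1) or the dosing listings (SAP Section 2.5.1.1.1). That would let readers see why a patient had 6 or 8 cycles, even if all patients have passed C6D15. It means two columns from imaging and hematology already scheduled. It also needs a visit window and a stated definition of normal counts: SAP Section 5.2.3.2 does not tie response evaluations to visits, and SAP Table 5-1 adds a neutrophil criterion that Protocol Table 14-1 lacks.
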